The intervention included exergaming using a Meta Quest head-mounted display. The Quest 2 was used until the release of the Quest 3 (October 2023). Participants received accessories to enhance accessibility, if comfort and accessibility were identified as an issue in the first intervention week. Accessories included a controller knuckle strap to accommodate people who were unable to grip or hold onto the controllers and head strap to enhance comfort by relieving frontal face or neck pressure and increasing the ease of equipping the device. For exercise, participants received consumer-available fitness games with rhythmic movements, which often included music. Participants were asked to exercise as possible each week, with a minimum goal of 150 min/week of moderate-intensity exercise and an advanced goal of 300 min/week of moderate-intensity exercise (further details can be found elsewhere)(12). Participants received a heart rate monitor (Polar OH1) to record their average exercise heart rate during each session, using an app from the Android and Apple Play Store (VR Health or VR Health Exercise Tracker). The participant or their caregiver took a screenshot after each exercise session and sent the screenshot to the study telecoach. When receiving a screenshot, the telecoach would respond with an inspiring emoji or verbal praise. The telecoach also provided weekly, theory-based, behavioral coaching and technical assistance through brief phone calls (~10 minutes) and text messages (12). Participants in the wait control group received the same intervention, after waiting for a 12-week period with their normal daily activities.

Procedures and Outcomes

Quantitative data were collected 3 times: baseline (week 0), mid-intervention or wait (week 7), and post-intervention or wait (week 13). A qualitative interview was conducted in week 13. All assessment procedures were conducted remotely, with study outcomes detailed elsewhere (12).

Purpose 1: Blood-related Cardiometabolic Health.

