Cardiometabolic health indicators included fasting insulin (µIU/mL), hemoglobin A1c (mmol/mol), high-sensitivity C-reactive protein (hsCRP; mg/L), fasting triglycerides (mg/dL), fasting cholesterol (mg/dL), and resting blood pressure (mmHg). These outcomes were measured by the participant and caregiver at home using a dried blood spot test kit, which was mailed to study staff and then mailed to the ZRT laboratory for analysis (12). Body weight was measured using a conventional bathroom scale that was shipped to participants. Blood pressure was measured using a sphygmomanometer (Omron 3 Series).

Purpose 1: Physical Activity Participation.

Self-reported activity was measured via the Godin Leisure Time Exercise Questionnaire (GLTEQ) at weeks 0, 7, and 13. The GLTEQ is a 7-day recall survey, scored using a health contribution metric, where only the moderate and vigorous components were scored using a multiplier of 5 and 9, respectively, and summed. An HC score of \geq 24 can equate to the minimum aerobic guideline of 150 mins/week of moderate exercise (13, 14).

Purpose 2: Feasibility Metrics.

Metrics included recruitment and adherence rates, trial management challenges related to technology and telehealth procedures, and intervention safety, assessed through number of adverse events (e.g., falls or injuries or problems) and potential intervention effects on pain and fatigue (measured by NIH Neuro-QoL Pediatric short forms)(12).

Analyses

As a preliminary study, the study is not powered for effectiveness. Findings will inform sample size and design considerations for an effectiveness trial. Analyses were performed in an intent-to-treat manner.

Primary Aim

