Descriptive statistics (means and SDs) were used to summarize participant baseline characteristics, and baseline variables were compared between groups using one-way analysis of variance. The primary analyses were conducted in an intent-to-treat manner, using linear mixed-effects models to compare between-and within-group changes (IS or WC). Models included fixed effects for the treatment group (IS vs. WC), time (baseline, week 7, and week 13), and their interaction. Random effects were included for participants to account for individual variability. Optimal model selection was based on Akaike's Information Criterion. Post hoc analyses were conducted using least-squared mean differences and 95% confidence intervals (CI). Mixed models for repeated measures data effectively handled missingness in outcomes, supplemented by multiple imputations by chained equation in Stata (StataNow/SE 18.5). Multiple imputations were performed by including outcomes, time, and auxiliary variables with 10 iterations. Estimations were combined using Rubin's rules (the STATA *mi* procedure). Blood spot specimens that were delayed longer than four weeks in the mail were excluded (due to potential degradation of the sample when not stored in ultra-low temperatures), resolved by missing imputation. Analyses were conducted using SAS software (version 9.4), with statistical significance set at p < 0.05.

Secondary Aim

For the feasibility metrics (ie, recruitment, retention, and adherence rates), no a priori criteria for acceptability will be established. Questionnaire results will be descriptively reported, and changes across time will be explored using general linear mixed models techniques, such as mixed models repeated measures analyses. An appropriate structure for the covariance matrix (eg, unstructured) will be selected for these models using the final data. Post hoc analyses will be performed using the Tukey-Kramer multiple comparisons test.

Tertiary Aim

The qualitative component will follow Charmaz's constructivist grounded theory framework, guided by the following philosophical assumptions: critical realism ontological perspective and an interpretivism epistemological perspective. Data will be analyzed by two investigators. Data

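### The stated imputation model leaves out treatment group; followed as written, it shrinks the group-by-time estimate toward zero

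*Combined protocol and SAP*

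**What the plan says.** All the relevant text is in the Combined protocol and SAP under Analyses, mostly in the Primary Aim paragraph.

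- Analysis model: "Models included fixed effects for the treatment group (IS vs. WC), time (baseline, week 7, and week 13), and their interaction".
- Role of imputation: "Mixed models for repeated measures data effectively handled missingness in outcomes, supplemented by multiple imputations by chained equation in Stata".
- Content of the imputation model: "Multiple imputations were performed by including outcomes, time, and auxiliary variables with 10 iterations". The auxiliary variables are not named.
- Pooling: "Estimations were combined using Rubin's rules".
- A planned source of missing values besides dropout: "Blood spot specimens that were delayed longer than four weeks in the mail were excluded". The same sentence says these gaps are filled by imputation.
- Use of the results, from the opening of Analyses: "Findings will inform sample size and design considerations for an effectiveness trial".

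Nowhere do the documents say that group, or group-by-time, was a predictor in the imputation model, or that imputation was done separately in each arm.

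**The concern.** An imputation model should contain at least the terms of the analysis model whose estimates are wanted. Here the term of interest is group-by-time. The imputation sentence names time, which is one analysis-model term, but not group. Group is not an auxiliary variable in the usual sense, because auxiliary variables are those outside the analysis model.

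If group is absent, imputed values in the immediate-start and waitlist arms come from the same regression. They differ by arm only as far as other predictors differ by arm, so mixing them with the observed values dilutes the contrast.

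Preliminary efficacy is the first objective, and the results are meant to feed the design of a larger trial. Required sample size varies as 1/effect². If planning used an estimate that kept 84% of the true effect, the planned size would be multiplied by 1/0.84² = 1.42, other inputs equal. The trial is not powered for effectiveness, so the issue is bias in the estimate and not loss of power.

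**Working it through.** The plan states no figure that could be reproduced here, so the check asks how much of a true effect survives under the imputation as described.

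**From the documents:** 1:1 allocation; visits at weeks 0, 7 and 13; analysis model with group, time and group-by-time; chained equations with 10 iterations; Rubin's rules.

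**Assumed:** 20 per arm; equal correlation r = 0.6 between visits; true effect 0.25 SD at week 7 and 0.5 SD at week 13; values missing completely at random in a share m; 10 imputations.

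**Closed form, only week 13 missing.** Impute week 13 from the person's own week-0 and week-7 values, without group.

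1. With equal correlation r, the slope on week 7 is b = r/(1 + r) = 0.6/1.6 = 0.375.
2. Randomisation makes the expected arm difference at baseline zero. The arm difference in imputed week-13 values is therefore b × (week-7 effect).
3. Let q = week-7 effect / week-13 effect = 0.25/0.5 = 0.5. The share kept is (1 − m) + m·b·q = 1 − m(1 − bq).
4. bq = 0.1875, so the share kept is 1 − 0.8125m.

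This uses the within-arm slope, so it is a close approximation to a regression fitted across both arms. Over r = 0.4 to 0.8 and q = 0 to 1, the share kept is 95–97%, 90–94%, 80–89% and 70–83% at m = 5%, 10%, 20% and 30%.

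**Simulation, same assumptions.** There were 2000 replicates per cell. Predictors were the outcome at the other two visits and one baseline auxiliary (correlation 0.3), with and without group. The analysis was a random-intercept model with group, time and group-by-time. Shares are relative to the full-data estimate in the same replicates.

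| | 5% missing | 10% | 20% | 30% |
|---|---|---|---|---|
| Closed form, week 13 only, no group | 95.9% | 91.9% | 83.8% | 75.6% |
| Simulated, week 13 only, no group | 96% | 92% | 84% | 75% |
| Simulated, any visit, no group | 94% | 88% | 76% | 62% |
| Pooled SE / empirical SD, week 13 only, no group | 1.04 | 1.09 | 1.17 | 1.25 |
| Pooled SE / empirical SD, any visit, no group | 1.08 | 1.16 | 1.32 | 1.49 |

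With group in the imputation model the share kept was 99–101%, and the standard-error ratio 1.00–1.05. The mixed model on observed data alone also kept 99–101%, with ratios of 0.99–1.01.

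**Second simulation, other missingness patterns.** This used 150 per arm to isolate bias, a true contrast of 0.50 SD, and no group in the imputation.

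| Pattern | 10% missing | 20% | 30% | 40% |
|---|---|---|---|---|
| Dropout | 0.44 | 0.41 | 0.37 | 0.31 |
| Both follow-ups missing | 0.44 | 0.40 | 0.34 | 0.30 |
| Intermittent, baseline included | 0.44 | 0.39 | 0.32 | 0.25 |

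With group included, the estimate was 0.49 to 0.53 throughout. At 20 per arm with both follow-ups missing, the estimates without group were 0.40 (20% missing) and 0.36 (30%), against 0.50 and 0.53 with group. With a true effect of zero and 30% missing, the estimate without group was 0.01 (Monte Carlo standard error 0.008), so no bias appears.

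**The case against.** The strongest reply is that the sentence summarises categories and is not a full specification. The code may have included group, and imputation by arm would not show in a list of predictors. This cannot be excluded. But the list names one analysis-model term and omits the central one, so either the method or its description needs correction.

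A second reply is that the mixed model may be the main analysis, with imputation only a supplement; the text names Stata for imputation and SAS for the analyses. An observed-data mixed model would indeed be free of this bias. The exact role of imputation is unclear, but Rubin's-rules pooling and the imputation of delayed blood spots show that imputed values enter at least some reported estimates.

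Third, richer predictors could stand in for group. If a variable such as the activity score differed by arm by 1 SD and was otherwise unrelated to the outcome, the share kept would rise from 84% to 87% at 20% missing and from 76% to 81% at 30%. With a 2 SD difference it would be 92% and 88%. The bias gets smaller but remains.

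Fourth, the bias is modest beside the noise of a pilot. With 20 per arm and r = 0.6, the full-data standard error of the week-13 change contrast is √[2(1 − 0.6) × 2/20] = 0.28 SD. The week-13-only bias is 0.5 × 0.8125m = 0.04, 0.08 and 0.12 SD at 10%, 20% and 30% missing, or 0.14, 0.29 and 0.43 of one standard error. When any visit can be missing at 30%, it is 0.5 × 0.38 = 0.19 SD, about 0.67 of one standard error. The omission would not manufacture a false positive. All this stands and limits the size, but a known and avoidable bias toward zero remains.

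**Conclusion.** The concern holds. The imputation as described omits the variable whose effect is being estimated, and following it attenuates any real group-by-time effect. Direction is clear in every scenario with a non-zero effect. Size depends on the missing rate, which the documents do not give: negligible with complete data, small at 5% missing or less, about 8–12% of the effect at 10% missing, and about 25–38% at 30% missing, under the main simulation's assumptions (20 per arm, r = 0.6, missing completely at random). The pooled standard errors are then too large for the attenuated estimate, so inference errs toward finding nothing. Confidence is medium, because the text does not show what the code did.

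**What to change.** First check the imputation code. If group was included or imputation was run by arm, correct the sentence to say so; nothing else is needed on this point.

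If group was omitted, add it to the imputation equation for the outcome at each visit, so that the arm difference can vary over time and group-by-time is preserved. Keep the other predictors few, given the pilot sample, and name the auxiliary variables. Re-run and pool again. Report the mixed model fitted to observed data only, either as primary or alongside, and state which analysis is primary. Choosing between those two is a matter of judgement; including group is not.

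The cost is one re-run and one corrected sentence. No new data are required.

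### The listed imputation model names neither the participant's other visits nor treatment group; on its natural reading it widens the error bars and pulls the effect toward zero

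*Combined protocol and SAP*

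**What the plan says.** All of this is in the combined protocol and SAP, under Analyses, Primary Aim.

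- Analysis model, fixed effects: "Models included fixed effects for the treatment group (IS vs. WC), time (baseline, week 7, and week 13), and their interaction".
- Analysis model, participant term: "Random effects were included for participants to account for individual variability".
- Missing data: "Mixed models for repeated measures data effectively handled missingness in outcomes, supplemented by multiple imputations by chained equation in Stata".
- Imputation model: "Multiple imputations were performed by including outcomes, time, and auxiliary variables with 10 iterations".
- Pooling: "Estimations were combined using Rubin's rules".
- A known source of gaps: "Blood spot specimens that were delayed longer than four weeks in the mail were excluded". The plan says these gaps are resolved by imputation.

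The section does not state the layout of the imputation data set, does not name the auxiliary variables, and does not give the number of missing values. The sample-size paragraph names a method but gives no N, SD or dropout rate.

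**The concern.** In chained equations, time can be a predictor only if it is a column. That is so when each participant contributes one row per visit; with one row per participant, the visit is part of the variable name. If the listed terms are complete, a missing week-13 value is drawn from the distribution for that visit, and the person's own week-0 and week-7 values of that marker are not used. The imputation model then omits the within-person correlation that the analysis model relies on.

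The specimen rule sharpens this. Insulin, HbA1c, hsCRP, triglycerides and cholesterol all come from the blood-spot kit, so a late specimen removes all five at that visit. In a visit-level row, only blood pressure, weight, the activity score and the unnamed auxiliaries remain as predictors. Once the gaps are filled, the mixed model treats the draws as data, and the protection claimed for it in "Mixed models for repeated measures data effectively handled missingness in outcomes" no longer applies to those values.

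Treatment group is not in the list either, although the group-by-time interaction is what the analysis estimates. The pilot is meant to inform the design of a later effectiveness trial, so a distorted effect, SD of change or within-person correlation would carry forward.

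**Working it through.** The plan has no figure to reproduce. **From the plan:** three visits (weeks 0, 7, 13), 1:1 allocation, a mixed model with group, time and their interaction plus a participant effect, and Rubin's rules. **Assumed:** n = 20 per arm, outcome SD 1, true week-13 effect δ = 0.5 SD, equal correlation ρ between visits, a fraction p of week-13 values missing, m = 10 imputations. The target is the between-arm difference in change from week 0 to week 13. Long means one row per visit; wide means one row per person.

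**1. Standard error, by hand.** Values are missing completely at random, group is in both imputation models, and auxiliaries are ignored.

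- Complete data: SE² = 4(1−ρ)/n. At ρ = 0.6: 4 × 0.4/20 = 0.080, SE 0.283 (simulated 0.282).
- Wide: weeks 0 and 7 explain R² = 2ρ²/(1+ρ) of week 13, so SE² ≈ 4(1−ρ)/n + (1+1/m) × 2p(1−R²)/[n(1−p)].
- Long: imputed values are unrelated to the person's other visits. The average correlation falls to ρ(1−2p/3) and nothing is explained, so SE² ≈ 4[1−ρ(1−2p/3)]/n + (1+1/m) × 2p/[n(1−p)].

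To this approximation n cancels from the ratio:

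| ρ | p | n × SE², long | n × SE², wide | SE ratio |
|---|---|---|---|---|
| 0.5 | 0.1 | 2.133 + 0.244 = 2.378 | 2.000 + 0.163 = 2.163 | 1.05 |
| 0.5 | 0.3 | 2.400 + 0.943 = 3.343 | 2.000 + 0.629 = 2.629 | 1.13 |
| 0.7 | 0.1 | 1.387 + 0.244 = 1.631 | 1.200 + 0.104 = 1.304 | 1.12 |
| 0.7 | 0.3 | 1.760 + 0.943 = 2.703 | 1.200 + 0.399 = 1.599 | 1.30 |

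**2. Standard error, by simulation.** Over 10-30% missing, the increase is 4-10% at ρ = 0.5 and 13-29% at ρ = 0.7, close to the hand figures. In a separate setting (400 trials, ρ = 0.6, nominal 20% missing completely at random):

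| Method | Average SE | Empirical SD | Coverage |
|---|---|---|---|
| Mixed model, observed rows | 0.307 | 0.302 | 95.8% |
| Wide, with group | 0.319 | 0.312 | 96.3% |
| Long, with group | 0.358 | 0.324 | 97.0% |

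The long SE is 0.358/0.319 = 1.12 times the wide one. The estimate's actual scatter rises less (0.324/0.312 = 1.04), so much of the widening here is an overstated SE. When missingness depends on earlier values alike in both arms, the SE ratio is 0.417/0.402 = 1.04 at ρ = 0.4, 0.383/0.337 = 1.14 at 0.6 and 0.349/0.239 = 1.46 at 0.8.

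**3. SD of change.** In long-imputed data the week-0 to week-13 correlation falls to about ρ(1−p), so the SD of change is inflated by √{[1−ρ(1−p)]/(1−ρ)}. At ρ = 0.5 this is √(0.55/0.5) = 1.05 for p = 0.1 and √(0.65/0.5) = 1.14 for p = 0.3. At ρ = 0.7 it is √(0.37/0.3) = 1.11 and √(0.51/0.3) = 1.30.

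**4. Bias with group included, long layout.**

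- Same dependence on earlier values in both arms: 0.00 to −0.03 SD (simulation error about 0.02).
- Opposite dependence in the two arms, ρ = 0.6: −0.21, −0.33 and −0.45 SD at 10%, 20% and 30% missing. At 20% missing, −0.26 to −0.44 SD over ρ = 0.4 to 0.8. Coverage across these settings is 79-92%. Wide imputation with group stays between −0.05 and 0.00.
- Only immediate-start participants with poor week-7 values more often missing (15-30% missing): +0.08 to +0.14 SD at ρ = 0.5 and +0.13 to +0.21 SD at 0.7 to 0.8.

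**5. Bias with group omitted, long layout.** Imputed week-13 values then carry no group difference, so the estimate is about δ(1−p) and the bias −pδ: 0.1 × 0.5 = 0.05, 0.2 × 0.5 = 0.10, 0.3 × 0.5 = 0.15 SD, all toward zero, with values missing completely at random. Simulation at 20% missing and ρ = 0.6 gives −0.095 SD in long layout, and −0.077 SD in wide layout if group is left out there too.

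**The case against.** The strongest reply is that one sentence of prose is not model syntax. It could loosely describe outcomes at each time point, which is one row per person. The unnamed auxiliaries could also include the same marker at other visits. In a long file, the baseline value alone would recover most of the information: at ρ = 0.7 it explains 0.7² = 0.49 of the variance, against 2 × 0.49/1.7 = 0.58 for weeks 0 and 7 together. This stands as a limit on certainty. A reader might infer that the visits were in fact treated as unrelated rows; the documents do not say so.

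A second reply is that the list cannot be read as complete for participant and incomplete for group. That is fair, and it is why group is handled separately above. If the list is complete, both omissions apply; if it is not, both need to be stated.

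A reader might also infer that the benefit is overstated, or that any dependence of missingness on earlier values biases the contrast. Neither is supported. Dependence that is alike in both arms nearly cancels, and where it differs between arms the sign follows the mechanism. Such a difference is plausible when only one arm is training, but it is not documented. The one named cause, mail delay, need not depend on earlier marker values.

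Finally, the trial is declared not powered for effectiveness, so lost power counts for little. The SE, the SD of change and the effect estimate still matter for planning. Because imputation is described as a supplement, an observed-data mixed model may already exist, although late specimens are said to be resolved by imputation.

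**Conclusion.** The point holds in conditional form. As listed, the imputation model does not match the analysis model: it names no participant information and no treatment group. If it was run in long layout with group added, the SE of the week-13 contrast is about 4-10% larger at ρ = 0.5 and 13-29% larger at ρ = 0.7, for 10-30% missing at 20 per arm, and bias is near zero unless missingness depends on earlier values differently by arm. If group was also left out, the effect is pulled toward zero by about 0.05 to 0.15 SD on a true 0.5 SD, without any special missingness mechanism. These sizes rest on assumed N, correlation and missing rates, and all of them shrink as the number of missing values falls. This is more than a gap in reporting, because a better method is available at little cost; it is not a finding that the results are wrong.

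**What to change.** Reshape to one row per participant before imputing, with weeks 0, 7 and 13 as separate variables. Impute each marker from its own values at the other visits plus arm, GMFCS level (the stratification factor) and one or two named auxiliaries, then reshape back for the mixed model. Work marker by marker: five blood markers, systolic and diastolic pressure, weight and the activity score make nine outcomes, or 27 columns over three visits, too many for one model in a pilot-sized sample. Report the mixed model on observed data beside the imputed result, with missing counts by arm and visit. State whether the 10 iterations are imputations or burn-in cycles.

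The cost is a sentence or two in the SAP, a few lines of Stata code and a re-run, with no new data. Estimates may change if the long layout was used. If a wide layout was used, correct the sentence to say so and confirm that arm was included.

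### Pairwise comparisons of pain and fatigue, which are safety measures, appear to get a Tukey-Kramer correction while benefit outcomes have none named, which lowers sensitivity to worsening symptoms

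*Combined protocol and SAP*

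**What the plan says.** Under Purpose 2 (Feasibility Metrics), safety has two parts. The first is "intervention safety, assessed through number of adverse events (e.g., falls or injuries or problems"). The second is "potential intervention effects on pain and fatigue (measured by NIH Neuro-QoL Pediatric short forms").

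Under Analyses, Secondary Aim, the plan states: "Questionnaire results will be descriptively reported, and changes across time will be explored using general linear mixed models techniques". It then sets the rule for follow-up comparisons: "Post hoc analyses will be performed using the Tukey-Kramer multiple comparisons test". It names no instrument, does not say which means form the Tukey-Kramer family, and makes no exception for safety measures.

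Under Analyses, Primary Aim, the corresponding sentence for the cardiometabolic and activity outcomes is: "Post hoc analyses were conducted using least-squared mean differences and 95% confidence intervals (CI"), "with statistical significance set at p < 0.05". No correction is named across contrasts, time points or outcomes.

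**The concern.** Familywise control protects against false positive claims. For benefit outcomes that is usually the error to guard against. For a symptom that may worsen under treatment, the costlier error is to miss a real change, and a familywise correction makes that error more likely.

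As written, the plan applies the correction to the symptom scores and names none for benefit. A pain or fatigue contrast estimated with the same precision as a benefit contrast would need a larger t statistic to be called significant, and its adjusted interval would be wider. Pain and fatigue are the only scaled safety outcomes in the plan; the other component is a count of adverse events. The plan says the findings will inform the design of an effectiveness trial, so how a symptom signal is read in this pilot has consequences.

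**Working it through.** The documents give no sample size, SD, effect size or power, so there is no stated figure to reproduce. The check sizes the penalty that the correction imposes.

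**Inputs from the documents**
- Significance level 0.05 (Primary Aim), taken as two-sided to match the 95% intervals.
- Two groups and three times. The Primary Aim model is described as: "Models included fixed effects for the treatment group (IS vs. WC), time (baseline, week 7, and week 13), and their interaction". If only times are compared there are k = 3 means and 3×2/2 = 3 pairs. If all group-by-time cells are compared there are k = 6 means and 6×5/2 = 15 pairs.

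**Assumptions, not in the documents**
- Error degrees of freedom: 38, with 18 and 76 as a range.
- Unadjusted power of 80% as the starting point, with 50% as a second case because the pilot is not powered for effectiveness.

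**Formulas**
- Unadjusted critical value: t(0.975; df).
- Tukey-Kramer critical value: q(0.95; k, df)/√2, where q is the studentized range quantile.
- Relative interval width: Tukey-Kramer critical value divided by unadjusted critical value.
- Per-comparison alpha: 2 × P(T > Tukey-Kramer critical value).
- Power: find the noncentrality that gives 80% (or 50%) at the unadjusted critical value, then recompute power at the Tukey-Kramer value from the noncentral t distribution.

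**Worked case, df = 38**
- Unadjusted: t = 2.024.
- k = 3: 3.449/√2 = 2.439, and 2.439/2.024 = 1.205.
- k = 6: 4.243/√2 = 3.000, and 3.000/2.024 = 1.482.

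| Means compared | df | Unadjusted t | Tukey-Kramer | Interval wider by | Per-comparison alpha | 80% power becomes | 50% power becomes |
|---|---|---|---|---|---|---|---|
| 3 | 18 | 2.101 | 2.552 | 21% | 0.0200 | 66% | 34% |
| 3 | 38 | 2.024 | 2.439 | 20% | 0.0195 | 67% | 35% |
| 3 | 76 | 1.992 | 2.390 | 20% | 0.0193 | 67% | 35% |
| 6 | 18 | 2.101 | 3.178 | 51% | 0.0052 | 44% | 17% |
| 6 | 38 | 2.024 | 3.000 | 48% | 0.0047 | 46% | 18% |
| 6 | 76 | 1.992 | 2.924 | 47% | 0.0046 | 47% | 18% |

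The result depends little on the assumed degrees of freedom and a great deal on which family is meant. The Secondary Aim speaks of changes across time, which fits the three-mean family better.

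**The case against.** Several points on the other side are sound and limit the concern.

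- **The instrument is not named.** The Secondary Aim refers only to questionnaire results. The instrument the plan actually calls a questionnaire is the Godin leisure-time questionnaire, a Purpose 1 outcome; the Neuro-QoL measures are called short forms. Read literally, the Tukey-Kramer rule might also reach one benefit outcome. Still, the Neuro-QoL forms are the only such instruments listed under Purpose 2, and nothing exempts them, so applying the rule to pain and fatigue remains the natural reading.
- **Silence is not a statement that no correction is used.** Tukey-Kramer is itself applied to least-squares mean differences, so the two post hoc sentences are not opposites. What can be said is that the Primary Aim names no correction.
- **Only pairwise contrasts are affected.** Tukey-Kramer does not alter the overall time or group-by-time test, the point estimates, the descriptive summaries or the adverse event counts. A reader might infer that the plan sets a higher bar for harm in general. The documents do not support that: at most it is true of pairwise comparisons of two symptom scores.
- **No decision hangs on it.** A reader might also infer that a non-significant rise in symptoms would be declared safe. The plan contains no such rule. It calls the questionnaire analysis exploratory and sets no acceptability criteria in advance.
- **The power figures are illustrative.** An unpowered pilot gives no basis for 80% as the true starting point, and the largest penalties need all 15 cell comparisons.

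The core survives. The plan prescribes a correction that reduces sensitivity for safety measures, gives no reason for it, and commits to no unadjusted interval for them. The exploratory status of the analysis weakens the case for familywise control here.

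**Conclusion.** The concern holds in limited form. On the natural reading, post hoc pairwise comparisons of pain and fatigue are Tukey-Kramer adjusted, and those of the benefit outcomes have no named adjustment. With three time means, the adjusted intervals are about 20-21% wider, the per-comparison alpha is about 0.02 instead of 0.05, and an illustrative 80% power drops to about 66-67%. With six group-by-time means, the intervals are about 47-51% wider. These figures assume a two-sided test and 18 to 76 error degrees of freedom; the 80% is an anchor, not a property of the trial.

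The effect is on how a symptom signal is read. It does not touch the primary analysis or any formal safety decision. It should be corrected, because the change is small and the present rule works against the purpose of a safety measure.

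**What to change.** In the Secondary Aim, name the Neuro-QoL pain and fatigue forms and state that:

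- they are reported as unadjusted between-group differences (immediate start minus waitlist) in change from baseline, with 95% confidence intervals, at weeks 7 and 13;
- Tukey-Kramer is not applied to them;
- safety is interpreted from the confidence limit in the direction of worsening, and a non-significant result is not taken as evidence of safety.

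This contrast also answers the safety question more directly. Pairwise comparisons of three time means pool the two arms, and a pairwise comparison of two of the six cell means is not a difference in change between arms.

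Tukey-Kramer may stay for questionnaires that are not safety measures. If it does, the plan should say which instruments it covers, including whether the Godin questionnaire is one of them, and which means form the family.

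The cost is a sentence or two of text and no new data. The downside is a few more false alarms on pain or fatigue, each of which can be reviewed clinically.
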